Approximately 53 patients with Type 2 diabetes mellitus (T2DM) with inadequate glycemic control receiving metformin at a dose of ≥ 1000 mg/day for at least 8 weeks prior to screening, will be randomized to 1 of 3 treatment groups.

Duration of treatment

Study duration will be at least 18 weeks, including a 1-week screening period, a 1-week run-in period, and a 16-week double-blind treatment period.

Investigational product, dosage, and mode of administration

Saxagliptin and matching placebo:

Saxagliptin 5 mg tablets or placebo matching saxagliptin will be administered orally QD for the 16-week double-blind treatment period.

Dapagliflozin and matching placebo:

Dapagliflozin 10 mg tablets or placebo matching dapagliflozin will be administered orally QD for the 16-week double-blind treatment period.

Other treatments

Metformin and Sulfonylurea (glipizide, glyburide, glimepiride)

Up to Visit 8 (Week 16), patients should continue to administer the same type and dose of metformin therapy they were using at study entry. Metformin and sulfonylurea will not be provided in pre-packaged kits by the Sponsor and will be sourced locally by the site and in accordance with the approved package labeling. Metformin and sulfonylurea should be administered and stored according to product and country-specific labelling.

Rescue therapy:

Patients who require rescue therapy should receive standard of care treatment; however, Bydureon 2 mg subcutaneously is highly suggested.

Statistical methods

Sample size estimate:

The primary comparison will be comparing EGP for saxagliptin 5 mg plus dapagliflozin 10 mg versus dapagliflozin 10 mg at Week 15.

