The primary endpoint (EGP) will be tested in a confirmatory fashion for saxagliptin 5 mg plus dapagliflozin 10 mg versus dapagliflozin 10 mg at the $\alpha=0.05$ (2-sided) level. The other comparisons (contrasts) will be tested in an exploratory sense at the $\alpha=0.05$ (2-sided) level. No multiplicity control is required.

The primary efficacy analysis will be performed using an analysis of covariance (ANCOVA) method for the change from baseline at Week 16, with terms for treatment group and baseline HbA1c subgroup ($\leq 8.5\%$ versus $> 8.5\%$), and baseline EGP value in the model. Point estimates and 95% confidence intervals will be calculated for the adjusted mean changes within each treatment group as well as for the differences in adjusted mean changes between treatment groups. A subject who terminates from the study early, is rescued, or does not have a Week 16 assessment for any other reason will not contribute to the primary analysis.

TABLE OF CONTENTS	PAGE
PROTOCOL SYNOPSIS.....	3
TABLE OF CONTENTS.....	11
LIST OF ABBREVIATIONS AND DEFINITION OF TERMS	16
1. INTRODUCTION	19
1.1 Background and rationale for conducting this study	19
1.2 Rationale for study design, doses and control groups.....	20
1.3 Benefit/risk and ethical assessment.....	24
1.3.1 Ethical safety considerations.....	24
1.3.2 Saxagliptin	25
1.3.3 Dapagliflozin.....	25
1.3.4 Potential benefits to patients	26
1.4 Study Design	26
2. STUDY OBJECTIVES.....	29
2.1 Primary objective	29
2.2 Secondary objectives	29
2.3 Safety objectives	32
2.4 Exploratory objectives	32
3. SUBJECT SELECTION, ENROLLMENT, RANDOMISATION, RESTRICTIONS, DISCONTINUATION AND WITHDRAWAL.....	33
3.1 Inclusion criteria	33
3.2 Exclusion criteria	34
3.3 Subject enrollment and randomization	36
3.3.1 Procedures for randomization.....	37
3.4 Procedures for handling incorrectly enrolled or randomized subjects.....	37
3.5 Methods for assigning treatment groups.....	38
3.6 Methods for ensuring blinding.....	38
3.7 Methods for unblinding.....	38
3.8 Restrictions	39
3.9 Discontinuation of investigational product	39
3.9.1 Discontinuation guidelines for protocol-defined major hypoglycemia episodes or recurrent non-major hypoglycemia episodes.....	40
3.9.2 Procedures for discontinuation of a subject from investigational product	40

3.10	Criteria for withdrawal.....	41
3.10.1	Screen failures.....	41
3.10.2	Withdrawal of the informed consent.....	42
3.11	Discontinuation of the study	42

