2. STUDY OBJECTIVES

2.1 Primary objective

Primary Objective:	Outcome Measure:
To compare the post-IP minus pre-IP endogenous glucose production (EGP) during the glucose turnover study in saxagliptin 5 mg plus dapagliflozin 10 mg vs dapagliflozin at Week 15.	
 Post-IP minus pre-IP EGP (mg/kg/min) during the glucose turnover study at Week 15.

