5.1.8 Glucose turnover study

A glucose turnover study will be performed according to schedule presented in Table 1. A glucose turnover study will be performed at Visit 3, which should be 5 to 14 days after the OGTT (Visit 2). An end of treatment glucose turnover study will be performed at Visit 7 and should be done approximately 10 days prior to the OGTT.

Patients will report to the study site after a 10-hour overnight fast and should be asked to void before beginning the glucose turnover study. At approximately 0600 (Time -180 minutes), a catheter will be placed into an antecubital vein and a primed (25 micro Curie [μCi] x FPG/100 up to a maximum of 50 μCi) – continuous infusion of [$3\text{-}^3\text{H}$]-glucose will be started]. The continuous infusion (0.25 $\mu\text{Ci}/\text{min}$) of [$3\text{-}^3\text{H}$]-glucose will be started and will be maintained throughout the study duration. A second catheter will be placed retrogradely into a vein on the dorsum of the hand, which will be placed in a heated box (50-60°C) for arterialized blood withdrawal. Prior to oral administration of study medication (saxagliptin, dapagliflozin, placebo), blood samples will be taken at the timepoints indicated in Table 3 for measurement of plasma glucose, insulin, C-peptide, glucagon, counter-regulatory hormones (i.e., plasma cortisol, growth hormone, adrenaline, and noradrenaline), and [$3\text{-}^3\text{H}$]-glucose specific activity. During the glucose turnover study, patients will receive assigned study medication 3 hours after the start of [$3\text{-}^3\text{H}$]-glucose infusion (Time 0). Blood samples will be obtained according to the timepoints indicated in Table 3 until the end of the study (Time 300 minutes/5 hours after drug is received). Metformin or metformin/sulfonylurea will **NOT** be taken until after the glucose turnover study has been completed.

Urine will be collected from the start of the study (Time -180 minutes) until Time 0 and again from Time 0 to 300 to measure urinary volume and urinary glucose concentration (to quantitate urinary glucose excretion). The glucose turnover study will end 5 hours after receiving study medication (Time 300 minutes) and patients will be given a meal and metformin or metformin/sulfonylurea and allowed to return home.

Table 3 Glucose Turnover Study

Timepoint (clock time)^a	Glucose	3-³H-glucose	Insulin/ C-peptide	Glucagon	CR hormones^b
-180 (0600)	X	X			
-30	X	X	X	X	X
-20	X	X			
-10	X	X	X	X	X
-5	X	X			

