8.2 Sample size estimate

This study will randomize patients to the following treatment arms (while continuing on metformin therapy):

- saxagliptin 5 mg + dapagliflozin 10 mg (n=21)
- dapagliflozin 10 mg + placebo for saxagliptin (n=21)
- placebo for dapagliflozin + placebo for saxagliptin (n=11).

The primary endpoint will compare the change in baseline EGP for saxagliptin (5 mg) plus dapagliflozin (10 mg) versus dapagliflozin (10 mg) at Week 16.

With 19 subjects per treatment group, there will be 90% power to detect a difference in mean EGP of 0.39 mg/kg/min between saxagliptin 5 mg plus dapagliflozin 10 mg and dapagliflozin 10 mg groups assuming a standard deviation of 0.32 using a 2 group t-test with a 0.050 2-sided significance level. Assuming that 10% of subjects in the primary comparison arms early terminate, are rescued, or do not have a Week 16 assessment for any other reason, a total of 21 subjects per treatment arm need to be randomized for each of the saxagliptin 5 mg plus dapagliflozin 10 mg and dapagliflozin 10 mg treatment arms. Approximately 11 subjects will be randomized to the placebo treatment arm for exploratory comparisons of saxagliptin 5 mg

plus dapagliflozin 10 mg to placebo (approximately 80% power), for a total of approximately 53 subjects randomized.

Assuming that 70% of screened patients will fail to meet screening criteria, a total of 177 patients will need to be screened.

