8.4 Outcome measures for analyses

The mean values will be compared between the treatment groups for the following measures:

1. Post-IP minus pre-IP EGP during glucose turnover study at Week 15.
2. Post-IP minus pre-IP EGP during glucose turnover study at Week 0 and the change from Week 0 to Week 15.
3. Pre-IP EGP during glucose turnover study at Week 15 and the change from Week 0 to Week 15.

4. Pre-glucose load EGP during the OGTT at Week 16 and the change from Week -1 to Week 16.
5. Change from Week -1 to Week 16 in post-glucose load EGP during the OGTT.
6. Change from Week -1 to Week 16 in Rd and Ra during OGTT.
7. Change from Week 0 to Week 16 in HbA1c.
8. Change from Week 0 to Week 15 in pre-IP plasma glucose during glucose turnover study.
9. Change from Week -1 to Week 16 in pre-glucose load FPG and post-glucose load PPG during the glucose turnover study.
10. Change from Week -1/0 to Week 15/16 in fasting plasma glucagon, C-peptide, and insulin during the glucose turnover study and OGTT.
11. Change from Week -1/0 to Week 15/16 in plasma glucagon, C-peptide, and insulin during the glucose turnover study and OGTT.
12. Change from Week 0 to Week 15 in post-IP minus pre-IP plasma glucagon, C-peptide, and insulin during the glucose turnover study.
13. Change from Week -1 to Week 16 in insulin secretion, beta cell function, and insulin sensitivity during OGTT.
14. Change in glucose oxidation and lipid oxidation during the baseline of the glucose turnover study, during the baseline of the OGTT, and post-glucose load during the OGTT.
15. Change in plasma ketones during the baseline of the glucose turnover study and OGTT.
16. Change from Week 0 to Week 15 in pre-IP, post-IP, and post-IP minus pre-IP in counterregulatory hormones during glucose turnover study.
17. Change from Week -2 to Week 16 in body weight and BMI; and percent body fat and fat distribution calculated from the DEXA scans.
18. Change from Week -1 to Week 16 in plasma GLP-1, GIP, and FFA during OGTT.
19. Change from Week -2 to Week 16 in FFA.
20. Change from Week 0 to Week 16 in waist to hip ratio, BP, and lipids.

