8.5.1 Analysis of the primary variable

The primary efficacy analysis will be performed using an analysis of covariance (ANCOVA) method for the change from baseline at Week 16, with terms for treatment group, baseline HbA1c subgroup ($\leq 8.5\%$ versus $> 8.5\%$), baseline treatment (metformin versus metformin/sulfonylurea) and baseline value in the model. Point estimates and 95% confidence intervals will be calculated for the adjusted mean changes within each treatment group as well as for the differences in adjusted mean changes between treatment groups. A subject who early terminates, is rescued, or does not have a Week 16 assessment for any other reason will not contribute to the primary analysis.

All inferential procedures of the secondary efficacy endpoints will be done at a 5% level of significance (2-sided).

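### The primary value comes from the Week 15 turnover study, but the primary analysis and its exclusion rule are tied to Week 16, so a valid value can be dropped for a later missed visit

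*Combined protocol and SAP*

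**What the plan says.** **Primary measure.** Section 2.1 names it as "Post-IP minus pre-IP EGP (mg/kg/min) during the glucose turnover study at Week 15", and item 1 of section 8.4 repeats "Post-IP minus pre-IP EGP during glucose turnover study at Week 15". Section 5.1.8 fixes the visit: "An end of treatment glucose turnover study will be performed at Visit 7 and should be done approximately 10 days prior to the OGTT". In Table 1 and section 4.2.2, Visit 8 (Week 16) has the double tracer OGTT. A patient on schedule has no turnover study there.

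**Time point of the analysis.** The synopsis, under Sample size estimate, agrees with the objective: "The primary comparison will be comparing EGP for saxagliptin 5 mg plus dapagliflozin 10 mg versus dapagliflozin 10 mg at Week 15". Section 8.2 does not: "The primary endpoint will compare the change in baseline EGP for saxagliptin (5 mg) plus dapagliflozin (10 mg) versus dapagliflozin (10 mg) at Week 16". Nor does section 8.5.1: "The primary efficacy analysis will be performed using an analysis of covariance (ANCOVA) method for the change from baseline at Week 16". The synopsis text on the primary variable also says Week 16.

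**Who is left out.** In 8.5.1, a subject who terminates early, "is rescued, or does not have a Week 16 assessment for any other reason will not contribute to the primary analysis". The synopsis applies the same exclusion to "A subject who terminates from the study early, is rescued, or does not have a Week 16 assessment for any other reason". The 10% attrition allowance in the synopsis and in 8.2 is defined by the same three reasons, again at Week 16.

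**General rule.** Section 8.5 uses values obtained before rescue and excludes those collected afterwards.

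**The concern.** The primary value is complete when the Visit 7 turnover study ends. The rule in 8.5.1 then makes its use depend on what happens over the following nine days or so (nominal days 103 to 112). A missed Visit 8 tells us nothing about whether the Week 15 value is valid, yet it removes that value.

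This sentence decides who enters the only confirmatory comparison. Two analysts could select different patients from the same data, depending on whether they take Week 16 literally or treat it as a slip for Week 15. The week label also matters in itself, because a different EGP measure does exist at Week 16: pre-glucose-load EGP in the OGTT, which is secondary (8.4, item 4). Read alone, the 8.2 sentence on change in EGP at Week 16 could be taken for that variable.

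**Working it through.** **1. The places side by side.**

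| Place | Time point |
|---|---|
| 2.1; 8.4 item 1; 5.1.8 | Week 15 (Visit 7) turnover study |
| Synopsis, sample size, primary comparison | Week 15 |
| Synopsis, sample size, attrition | Week 16 |
| 8.2, comparison and attrition | Week 16 |
| Synopsis, primary variable; 8.5.1 | Week 16, as change from baseline |

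**2. Who can lose a valid Week 15 value under the literal rule.**

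- A patient who completes Visit 7 and misses Visit 8. This needs no assumption about rescue.
- A patient who terminates after Visit 7.
- A patient rescued after Visit 7. This case depends on the calendar.

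**3. Calendar for rescue after Visit 7.** Inputs are Table 1, its footnotes a and j, and section 4.2. I assume that the Visit 7 study serves as the turnover study required before rescue.

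- Visit 7: day 103 ± 5, so days 98 to 108.
- Repeat FPG 3 to 5 days later: 103 + 3 = 106 to 103 + 5 = 108.
- Pre-rescue OGTT under footnote j, 5 to 14 days after the turnover study: 103 + 5 = 108 to 103 + 14 = 117.
- Visit 8: day 112 ± 4, so days 108 to 116.

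On nominal days, the assessments required before rescue therefore fall almost wholly within the Visit 8 window. A gap needs an early Visit 7 or the footnote a timing (3 to 5 days). With Visit 7 on day 98, the OGTT could come from 98 + 5 = 103 (footnote j) or 98 + 3 = 101 (footnote a). That is 108 − 103 = 5 or 108 − 101 = 7 days before the window opens. The two footnotes give different intervals and should be reconciled; I take no view on which is right.

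**4. Size.** The primary arms hold 21 + 21 = 42 patients. One patient is 1/42 = 2.4%; two are 2/42 = 4.8%. The documents give no count, so these are units of scale and not estimates.

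**5. Power.** Inputs from 8.2: difference 0.39, SD 0.32, two-group t-test, two-sided 0.05; standardised difference 0.39/0.32 = 1.219. The plan states 90% power with 19 per arm. I do not reproduce that: the noncentral t distribution gives 95.5% at 19 per arm, and 16 per arm suffice for 90%. That discrepancy is a separate matter.

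| Evaluable per arm | Power, SD 0.32 |
|---|---|
| 21 / 21 | 97.1% |
| 20 / 21 | 96.7% |
| 20 / 20 | 96.4% |
| 19 / 19 | 95.5% |

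At an assumed SD of 0.36, where 19 per arm does give about 90%, power is 92.9% at 21 per arm and 90.1% at 19. Even if the rule consumed the whole step from 21 to 19, power would stay at or above the stated 90%.

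**The case against.** **It may be only a label.** The table of contents still calls Visit 7 Week 16a and Visit 8 Week 16b. Week 16 in 8.5.1 may be a leftover that covers both visits, in which case no Week 15 value is lost. This plausibly explains the origin. It does not cure the text: the body now separates Weeks 15 and 16, and nothing says that Week 16 means Visit 7.

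**The exclusion was declared.** The sample size allows 10% for exactly these losses, so the rule is deliberate. That is so, and the sponsor may choose to exclude patients without a usable primary value. But the allowance repeats the wrong week and gives no reason to discard a value already obtained.

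**There is no strict clash with 8.5.** That section limits which values may be used; it does not say that every pre-rescue value must enter the primary analysis. Also, the words on any other reason can be read to mean that rescue excludes only when the assessment is missing. Both points stand as readings. They show that the text permits more than one analysed population.

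**Partial safeguards exist.** Section 3.3.1 replaces early discontinuers, and 8.5.4 allows a sensitivity analysis on all available data. Replacement protects numbers but not against selection, and the sensitivity analysis is optional.

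A reader might infer that the plan discards primary data from rescued patients in general. It does not. Those rescued from Week 8 or Week 12 draws have no on-schedule pre-rescue Week 15 value, and 8.5 would exclude their later values anyway.

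**Conclusion.** The point holds as an inconsistency that is wrong as written and minor in size. The time point and the exclusion rule of the primary analysis do not match the primary measure. Applied literally, they can remove a valid Week 15 value because of a later missed visit or termination or, rarely, a later rescue.

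Few patients are likely to be affected, since the interval is short and the rescue route is nearly empty on nominal days. This rests on Table 1's nominal days and windows and on the literal reading of 8.5.1.

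Two stronger conclusions are tempting and unsupported. One is that the trial loses meaningful power: the figures above show that it does not. The other is that the rule biases the comparison in a known direction: the documents give no number of affected patients, no split by arm, and no relation between missing Visit 8 and EGP.

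**What to change.** 1. In the synopsis (sample size attrition text and primary variable text), 8.2 and 8.5.1, change the primary time point and the attrition and exclusion wording from Week 16 to the Week 15 (Visit 7) glucose turnover study.

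2. Replace the exclusion sentence in the synopsis and 8.5.1 with:

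> Every FA patient with a Week 15 (Visit 7) glucose turnover value obtained before any rescue medication contributes to the primary analysis, regardless of a missed Week 16 visit or of rescue or termination after that study; patients without such a value do not contribute.

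   This agrees with the pre-rescue rule in 8.5.

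3. In the same edit, make the response variable in 8.5.1 the Week 15 post-IP minus pre-IP EGP. Changing the week alone would leave a change from baseline, and the Week 0 to Week 15 change is a secondary outcome (2.2). State which Week 0 term enters the model: post-IP minus pre-IP EGP, or pre-IP EGP. Section 8.1 defines baseline as before the first dose, which only the pre-IP value satisfies.

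4. Report exclusions from the primary analysis by arm and reason.

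The sensitivity analysis in 8.5.4 can stay as planned. One that adds pre-rescue and early-termination turnover values would be optional and additional, not a replacement.

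Cost: wording only, with negligible extra analysis work and no new data. The change should be made before unblinding.

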8.5.2 Analysis of the secondary and exploratory variables

The continuous secondary endpoints will be analyzed using a repeated measures model when the endpoints are collected at visits in addition to Week 16. A longitudinal repeated measures analysis (using a MIXED model) for the change from baseline at Week 16, with terms for treatment group, baseline HbA1c subgroup ($\leq 8.5\%$ versus $> 8.5\%$), baseline treatment (metformin versus metformin/sulfonylurea) baseline value, time (each relevant visit), the interaction of treatment and time, and the interaction of baseline value and time in the model. Point estimates and 95% confidence intervals will be calculated for the adjusted mean changes within each treatment group as well as for the differences in adjusted mean changes between treatment groups.

The continuous secondary endpoints will be analyzed using an ANCOVA model like the primary endpoint when the endpoints are collected at baseline visit (Visit 3) and Week 16 only.

8.5.3 Subgroup analysis

The subgroup analysis will be performed according to the baseline HbA1c cutoff: $\leq 8.5\%$ or $>8.5\%$.

Subgroup analyses will be analyzed in an exploratory fashion with respect to the primary efficacy endpoint as was done for the original analysis with terms for treatment group and baseline value, but for the applicable subset of subjects. Interaction tests will be performed by using the same primary analysis model with terms for treatment group, baseline HbA1c subgroup ($\leq 8.5\%$ or $>8.5\%$), and baseline value but with treatment-by-HbA1c subgroup interaction terms added.

8.5.4 Sensitivity analysis

Sensitivity analyses may be conducted using all available data and including a time varying covariate that indicates rescue status.

8.5.5 Safety analyses

Descriptive statistics of demographic and other baseline characteristics will be calculated. Safety and tolerability will be assessed using standard tabulations of AEs and AEs of special interest (using predefined lists of preferred terms), laboratory values and marked abnormalities, vital signs, physical examinations, and ECGs. The number and percentage of patients with hypoglycemia will be tabulated and presented by treatment group.

8.6 Interim analysis

No interim analysis on the efficacy or safety parameters is planned for this study.

9. STUDY AND DATA MANAGEMENT

9.1 Training of study site personnel

The Investigator will ensure that appropriate training relevant to the study is given to all of these staff, and that any new information relevant to the performance of this study is forwarded to the staff involved.

The Investigator will maintain a record of all individuals involved in the study (medical, nursing, and other staff).

Monitoring of the study

A UTHSCSA Compliance Monitor:

- Will review the study progress, protocol deviations, and adverse events every 2-4 weeks.
- Confirm that facilities remain acceptable
- Confirm that the investigational team is adhering to the protocol, that data are being accurately and timely recorded, and that study drug accountability checks are being performed

- Perform source data verification including verification of informed consent of participating patients.
- Ensure withdrawal of informed consent to the use of the patient's biological samples is reported and biological samples are identified and disposed of/destroyed accordingly, and the action is documented, and reported to the patient.

